The primary aim of this sub-study “ATN 144b Dried At-Home Blood Science” (Project DABS) is to leverage our current ATN 144 SMART recruitment and screening methods and patient population to develop and test DBS implementation procedure to promote home-based DBS collection and change the landscape of adherence research in youth living with HIV. Additionally, if feasible, DBS collection implementation may enhance ATN 144 SMART protocols for obtaining VL, both at enrollment and follow-ups. DBS

PROTOCOL TITLE: ATN 144 SMART

collection has the potential to help identify additional youth who are eligible for ATN 144 SMART, thereby increasing enrollment in this difficult patient population, and aid in improving retention for those who do not provide VL via a clinic or testing facility.

Specific Aims:

1. Assess the suitability, feasibility and acceptability of using DBS collection to obtain timely data on VL monitoring for HIV-positive youth between 15-24 years old.
2. Examine barriers and facilitators of using DBS collection for VL monitoring and expand access to VL monitoring for HIV-positive youth between 15-24 years old.
3. Adapt VL collection methods (i.e., construction and distribution of at-home testing kits and surveys, tracking and monitoring testing kit completion, tracking and monitoring at-home survey completion) for DBS in this population.
4. Use a central laboratory to measure VL and evaluate the accuracy and lower limit of detection of a DBS. Currently, the lower limit is estimated at 500 to 800 copies/mL. This is not consistent with the latest definition of VL below detection (e.g., 200 copies/mL).
5. Explore utilizing DBS collection to screen and monitor VL for ATN 144 SMART and future protocols.

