Hemaspot™-HF Blood Sampling Kit. Once the protocol team has received the subject's consent/assent to participate, the protocol team will mail the HemaSpot™-HF blood sampling kit to the address provided by the participant. The HemaSpot-HF collection kit is a cartridge with absorbent paper covered by a surface with a small spot to direct blood onto the paper. After drawing 3 drops of blood, the paper is sufficiently saturated; a desiccant within the cartridge rapidly dries the blood to preserve it for transit to the laboratory, which can occur at ambient temperature. The HemaSpot cartridge will be placed within appropriately labeled specimen packaging and returned to the PRIDE Health Research Consortium at Hunter College with prepaid mailing labels. After receiving kits, study staff will store samples to be sent to the laboratory for testing in batches. The kit contains instructions on how to perform the blood collection and properly store and handle the kit (see below). Participants will also receive a brief survey that contains an instructional video along with the kits received and sent dates to allow for more accurate tracking and monitoring of the samples in transit. The Caliendo Molecular Laboratory at the Miriam Hospital in Rhode Island will then perform a quantitative analysis of VL using the participant's DBS sample. We will use the AmpliPrep/COBAS TaqMan HIV-1 Test, v2.0 assay to analyze samples collected.

Figure 2. Spot*On Sciences' HemaSpot™-HF blood collection sampling kit instructions.

Online Computer Assisted Self-interviewing (CASI). The protocol team will send an online CASI questionnaire, supported by the Qualtrics platform, via a hyperlink to the email and phone number provided by the subject. The online CASI will ask questions pertaining to the following: demographics, modules on suitability, feasibility, and acceptability of using DBS, social determinants of health, HIV cascade, and the last section focused on feedback for future trials.

Web-based CASI Measures	Baseline
Section A: Demographics (Aims 1, 2, and 5)	
ATN Standard Domain: Demographic Characteristics	X
Section B: Suitability, Feasibility, and Acceptability (Aim 1)	
Module 1: Suitability	
Intervention Appropriateness Measure (IAM)	X
Module 2: Feasibility	
Feasibility of Intervention Measure (FIM)	X

PROTOCOL TITLE: ATN 144 SMART

At-Home Dried Blood Spots Testing Usability Scale	X

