11.0 Local Number of Subjects

We will enroll 120 HIV-positive youth living with HIV aged 15-24.

Sub-Study:

This study aims to enroll 50 YLH, ages 15-24, nationally.

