Data Analysis Plan. To assess the feasibility of using DBS we will examine descriptive data to determine how many participants returned the DBS specimen. Descriptive statistics, frequencies, means and standard deviations, will be used to describe the samples' demographic characteristics as wells as perceptions of their suitability, feasibility and acceptability. To identify potential barriers and facilitators of testing response rates we will conduct exploratory analyses comparing differences in demographics and perceptions in youth who did return the DBS specimen versus those who did not. We will examine proportional differences using chi-square tests for categorical variables and mean differences using t-tests for continuous outcomes ($\alpha = 0.05$). For the suitability, feasibility and acceptability scales we will calculate Pearson correlation coefficients to examine the relationship between these variables and potential barriers and facilitators. Point bi-serial correlations will be used when comparing the scales and dichotomous variables.

Confidentiality. All laboratory specimens, questionnaires, evaluation forms, reports, and other records will be identified by a coded number only, to maintain participant confidentiality. All records with personally-identifying information will be kept in a locked, limited access area (such as a locked file cabinet). All computer entry and networking programs will be done with coded numbers only. Clinical information will not be released without written permission of the participant (and parent or legally authorized representative, when applicable), except as necessary for monitoring by the ATN SIU or NICHD.

To further protect the privacy of the study participants, the ATN SIU has obtained a Certificate of Confidentiality from the U.S. Department of Health and Human Services. With this Certificate in place, the ATN SIU researchers cannot be forced to turn over identifying information about a study participant in any Federal, State, or local criminal, administrative, legislative, or other proceedings. This Certificate does not prevent a study participant from volunteering to turn over their research information, nor does it prevent researchers from providing research-related information to others when requested by the study participant.

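### The only objective feasibility measure in DABS is kits returned, an upper bound on the timely viral load results that Aim 1 concerns

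*Protocol*

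**What the plan says.** Protocol section 1.0 gives DABS Aim 1 as: "Assess the suitability, feasibility and acceptability of using DBS collection to obtain timely data on VL monitoring for HIV-positive youth". Aim 4 adds the laboratory side: "Use a central laboratory to measure VL and evaluate the accuracy and lower limit of detection of a DBS".

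The DABS data analysis plan in section 16.0 takes up feasibility with: "To assess the feasibility of using DBS we will examine descriptive data to determine how many participants returned the DBS specimen". It then describes demographics and participants' perceptions, and it explores barriers and facilitators by comparing "youth who did return the DBS specimen versus those who did not". The planned size, in section 11.0, is: "This study aims to enroll 50 YLH, ages 15-24, nationally".

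Section 5.0 describes what happens to a kit. The participant collects the blood at home ("After drawing 3 drops of blood, the paper is sufficiently saturated"), the cartridge dries it, and the kit is posted back. Then "study staff will store samples to be sent to the laboratory for testing in batches". The same section lists a feasibility scale, a usability scale and a qualitative interview. The SAP supplied contains no DABS analysis.

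**The concern.** Aim 1 is about getting VL data in time to be useful, while the planned count stops when the kit arrives back at the study office. A card that is under-filled, poorly dried or rejected by the laboratory still counts as returned. So does a good card whose result comes late because samples were held for batching.

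The sub-study is meant to explore whether home DBS could supply VL for SMART screening and follow-up (sections 1.0 and 5.0). For that purpose the useful quantities are results per kit mailed and time to result. If only the return rate is reported, readers planning later work have no objective estimate of either.

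**Working it through.** **Inputs from the documents**
- Objective feasibility measure: participants who returned a specimen (Protocol section 16.0, DABS data analysis plan).
- Planned sample: 50 (section 11.0). Kits are mailed after consent (section 5.0), so I take 50 as the number mailed a kit.
- Steps before a result: self-collection, drying, posting, storage, batching and assay (section 5.0).
- Expected return rate, valid-result rate, turnaround limit and feasibility threshold: none stated.

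There is no stated figure to reproduce, so the check is a bound followed by an illustration.

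**Bound.** A laboratory result requires a returned kit. With N participants mailed a kit, return proportion r, and y the share of returned kits that give a result:

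p(result) = r × y ≤ r, and the gap is r × (1 − y).

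The planned summary estimates r and carries no information about y.

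**Illustration.** The values of r and y are assumptions; N = 50; intervals are exact (Clopper-Pearson) 95% CIs.

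| Returned (plan reports) | Assumed y | With a result | Proportion (95% CI) |
|---|---|---|---|
| 40/50 = 80% (66.3–90.0%) | 100% | 40 | 80% (66.3–90.0%) |
| same | 90% | 36 | 72% (57.5–83.8%) |
| same | 80% | 32 | 64% (49.2–77.1%) |
| same | 60% | 24 | 48% (33.7–62.6%) |
| same | 50% | 20 | 40% (26.4–54.8%) |
| 45/50 = 90% (78.2–96.7%) | 80% | 36 | 72% (57.5–83.8%) |
| same | 60% | 27 | 54% (39.3–68.2%) |

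In the first five rows the plan would report 80% each time. A time limit on results could lower the last column further, but no limit is given from which to compute this.

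**Do the other feasibility data fill the gap?** No. The scales record perceptions. The interview is offered only after both the kit and the survey have been received, so it does not reach non-returners, and it does not measure yield or turnaround.

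**Are the data available?** Partly. VL is measured and shared with participants (sections 5.0 and 7.0), and kit received and sent dates are collected to track samples in transit (section 5.0). Neither a result date nor a record of specimen rejection is described.

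**What counts as a result?** Section 1.0 puts the DBS lower limit at 500 to 800 copies/mL, against a threshold of 200. A sample reported as below that limit was assayed successfully, yet it cannot be placed above or below 200. This may be common: recruits include youth who screened ineligible for SMART (section 12.0), and a suppressed VL is one route to ineligibility (section 13.0). Yield therefore needs a definition before it can be counted.

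**The case against.** The strongest reply is that the protocol separates participant feasibility from laboratory performance. Aim 4 covers the assay, and return is a natural measure of whether youth will do the test at home. A return rate reported as a return rate is not biased, and the pilot also collects feasibility and usability scores and interviews.

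Much of this stands. Return belongs in the report, and it is not the whole feasibility assessment. But Aim 1 itself refers to timely VL data, and Aim 4 does not close the gap: section 16.0 contains no analysis for it, and accuracy and detection limit are in any case not the same as the share of kits giving a result.

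Three stronger readings are tempting, and the documents do not support them.
- A reader might infer that the returner versus non-returner comparison is flawed in the same way. Its stated purpose is to find barriers and facilitators of response rates, and for that the grouping is right. Pooling non-returners with laboratory failures would mix two mechanisms.
- A reader might infer that DABS decides whether SMART adopts DBS. The language in sections 1.0 and 5.0 is exploratory and conditional.
- A reader might infer that the fix is wording alone because every data item exists. The missing result date and rejection record leave that unproven.

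**Conclusion.** The point holds in a limited form. The one objective feasibility measure is an upper bound on the proportion of participants for whom home DBS yields a VL result, and turnaround is not analysed at all. The direction follows from the sequence of steps and needs no assumption. The size is unknown: with 40 of 50 returned, a yield between 100% and 50% would put the true figure anywhere from 80% to 40%, but those rates are mine.

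A reader might go further and conclude that the sub-study would declare home DBS feasible while many samples failed. The documents state no feasibility threshold or go/no-go rule and no expected failure rate, so neither half of that statement can be shown.

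The consequence is confined to a descriptive result in a 50-person pilot. No SMART hypothesis, error rate or safety provision is affected. The change is still worth making, because it is cheap and gives the quantity that Aim 1 names.

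**What to change.** In the DABS data analysis plan (Protocol section 16.0):

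1. Over all participants mailed a kit, report the number and proportion, with 95% CI, (a) returning a kit and (b) having a reportable laboratory VL result. Make (b) the main objective feasibility measure.
2. Report median days from kit mailing to result.
3. Define a reportable result in advance. State that a result below the DBS assay's lower limit counts as reportable and is shown separately. Also show how many results can be classified against 200 copies/mL.
4. Log the result date and any specimen rejection, if these are not already recorded.
5. Keep returned versus not returned as the grouping for the response-rate comparison, and list returned but unusable samples descriptively.

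The cost is a few sentences of plan text and one or two extra data fields. The feasibility figure may look less favourable. Turnaround will reflect the study's own batching as well as home collection, and the report should say so.

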17.0 Provisions to Monitor the Data to Ensure the Safety of Subjects*

This research involves no more than Minimal Risk to subjects.

The protocol has a Data Safety Monitoring Plan and is reviewed semiannually by a Study Monitoring Committee.

The Scale-It-Up (SIU) U19 Data Safety and Monitoring Plan will utilize a single monitoring system for all SIU protocols (including SMART) in order to harmonize review standards across protocols. The review process of the most vulnerable protocol will be applied to all SIU protocols thereby ensuring adequate oversight. We propose utilizing an independent study monitoring committee (SMC). A SMC was selected as the Clinical Research Management (CRM) as it is the highest level CRM needed for the most vulnerable SIU protocol. The proposed SMC will be composed of three independent experts who possess the relevant expertise (e.g., HIV-related research and prevention, adolescent medicine, and sexual health) to evaluate each SIU protocol and whom do not have a conflict of interest. [name], [name], and [name] have formally agreed to serve on the SIU SMC. Together, they represent an academically diverse and highly experienced team capable of providing the necessary foresight and oversight to ensure data safety monitoring plans are diligently designed and implemented. SIU has the appropriate funding available to financially support the activities of the SMC. The SMC will review each research protocol and plan for data and safety monitoring every 6 months, with additional ad-hoc reviews as necessary. All SMC meetings and reviews will be held via telephone conference.

Adverse Events Reporting. Data for monitoring participants' safety will be captured within the Access database as part of the required study data. There are no additional study-specific reporting requirements. Information on unexpected events including serious adverse effects will be reported to the sIRB.

Sub-Study:

This study does not involve more than minimal risk to subjects.

18.0 Provisions to Protect the Privacy Interests of Subjects

We protect the privacy interests of participants in several ways. The team of research staff working on this study is trained and committed to advancing the rights, regard, and sexual health of youth living with HIV. We utilize sex-positive and non-judgmental approaches in developing standard operating procedures, surveys, and intervention guides. Staff training in contacting participants highlights creating a comfortable interaction for the participant, having good listening skills, adopting non-judgmental approach, paying close attention to detail, being very knowledgeable about the study so as to answer questions participants may have, and being sensitive and flexible to participant's personal situations that may impede completing a study assessment within their window. The research team is permitted to access participants' information only

after completion of a comprehensive training followed by post-training mocks and feedback.

19.0 Compensation for Research-Related Injury

The research and the sub-study do not involve more than Minimal Risk to subjects.

20.0 Economic Burden to Subjects

Research subjects are responsible for co-pays that may be incurred during any medical visits to a healthcare provider for viral load testing.

Sub-Study: The protocol team expects enrolled subjects to incur no financial costs as a result of their participation in this study.

21.0 Consent Process

Once it is determined that a potential participant may qualify for the study, study details will be discussed and all questions answered by phone. During this screening process, potential participants will be asked if they verbally consent to being screened and complete a phone screener. Electronic informed consent/assent and HIPAA authorization will be obtained from each participant before any study-related procedures are performed. Since this is a nation-wide study, the consent process is not done in person. Instead participants receive the consent/assent form via an emailed link from Qualtrics. The electronic consent/assent form contains a set of “True or False” statements at the end of the form to verify that the participant understands the study and its components. The consent/assent form asks the following questions:

1. True or False: Participating in the study is my choice and I can choose to stop participating at any time, even if I agree today.
2. True or False: Every participant will be asked to complete online surveys and provide HIV viral load results or complete HIV viral load testing every three months for the full year of this study.
3. True or False: If I ask, the SMART research team may contact my provider to share information such as whether I need a refill of my medications or other quality of life matters.
4. True or False: The HIV viral load testing performed for this study is free. I am not responsible for the cost of a study related HIV viral load test.
5. True or False: If I already have HIV viral load results I can provide these to the research team if the results are recent.

If one response is incorrect, the form redirects to a page that contains all of the correct responses to the above statements for the participant’s review.

Non-English Speaking Subjects. Eligibility includes criteria that participants must speak English. No separate plan for obtaining consent is needed for non-English speakers.

Sub-Study:

Informed Consent. Once it is determined that a potential subject may qualify for the study, study details will be discussed through the online consenting process and all questions answered by email/phone. During this consenting process, potential subjects will be asked if they consent to complete an online survey, complete the at-home DBS testing component, and complete an exit qualitative interview. Electronic informed consent/assent will be obtained from each subject before any study-related procedures are performed. Additional electronic consent/assent will be provided for audio recordings as part of the qualitative exit interviews. Since this is a nation-wide study, the consent process is not done in person. Instead subjects receive the consent/assent form via an emailed link from Qualtrics. The electronic consent/assent form contains a set of “True or False” statements at the end of the form to verify that the subject understands the study and its components. The consent/assent form asks the following questions:

- True or False: Participating in the study is my choice and I can choose to stop participating at any time, even if I agree today.
- True or False: Every subject will be asked to complete a one-time online survey and provide DBS specimen for the participation of this study.
- True or False: The HIV viral load testing performed for this study is free. I am not responsible for the cost of a study related HIV viral load test.

If one response is incorrect, the form redirects to a page that contains all of the correct responses to the above statements for the subject’s review.

22.0 Process to Document Consent in Writing

Consent will be obtained electronically using a consent or assent form which details all study procedures and expectations for participation. The participant will electronically sign the consent/assent form, which is then stored on Qualtrics. The consent and assent forms were written using the template consent document (HRP-502).

Sub-Study:

Consent will be obtained electronically using a consent or assent form which details all study procedures and expectations for participation. The subject will electronically sign the consent/assent form, which is then stored on Qualtrics. The consent and assent forms for this study comply with Florida State University’s template consent document (HRP-502).

Waiver or Alteration of Consent.

For children, age 15-17, whose parents or legal guardians already know about the children’s HIV status and who if told would not place the children at risk of harm, parental permission for these children will be obtained. We are requesting a waiver of parental consent for youth who indicate that involving their parent or guardian may put them at risk of harm.

We are requesting a waiver of parental consent for participants aged 15-17. Our research protocol is designed for conditions or for a subject population for which parental or

PROTOCOL TITLE: ATN 144 SMART

guardian permission is not a reasonable requirement to protect the YLH, age 15 – 17. Youth will be completing daily phone calls and online surveys that discuss sensitive topics such as their sexual behavior, sexual orientation, etc. It is also expected that there will be participants who have not disclosed their HIV status to parents/legal guardians, and the parents/legal guardians will not be aware of the subject's sexual orientation or risk behaviors. A requirement for parental permission in this type of study could not only affect a person's willingness to participate, but could also potentially impact the ability of researchers to engage in this type of HIV-related research with youth. Parental permission would put those youth whose parents do not already know about their sexual behavior and/or HIV status, infrequency of HIV-related care, at risk of their parents learning about this by the nature of requesting their permission to participate in a study of this kind. This may then place these youth at risk for parental harassment, abuse or expulsion from the parental home. Requiring parental permission could not only place these youth at increased risk of harm, but it would also substantially limit the generalizability of our research.

Our justification for this waiver is informed by prior research with the target population, which has demonstrated risks of parental victimization during coming out or discussions of sexual orientation. Most young men who have sex with men (YMSM) are unwilling to ask their parents' permission to be in an HIV-focused study and those who are willing are significantly different on key variables. In addition, research suggests that YMSM have the capacity to make an informed decision regarding participation (e.g., appreciation of risks/benefits to themselves, understanding research components such as randomization) despite this not meeting the legal definition of consent. As shown in prior research, parents with LGBT-identified children appreciate the rationale for waivers of their permission when the study and its purpose are explained. This evidence supports the fact that YMSM are a population for whom parental or guardian permission is not a reasonable requirement to protect the participants and a waiver of parental permission is appropriate under 45 CFR 46.408(c). This determination was further supported by the fact that this study does not expose participants to greater risk than encountered in everyday life, and therefore the waiver could also be approved under 45 CFR 46.116(d) based on the evidence described above that the research is not possible if parental permission is required. Additionally, consistent with national policy recommendations from the Society for Adolescent Medicine, requiring parental permission for the proposed study would have a number of possible negative effects, including: (1) reducing the validity of the findings by effectively eliminating potential participants unwilling to share permission forms with their parents/guardians; (2) increasing risk to some youth whose parents have a negative response to the material in the permission forms that would suggest their child has a minority or alternative sexual orientation; and (3) adding little in the way of actual subject protection, given the minimal risk of study participation.

Under 45 CFR Part 46.4116 (c), an IRB has the authority to waive parental permission if it determines that “a research protocol is designed for conditions or a subject population for which parental or guardian permission is not a reasonable requirement to protect the subjects” and “an appropriate mechanism for protecting the children who will participate as research subjects is substituted” and “that the waiver is not inconsistent with Federal, state, or local law.” The study procedures involve research on individual on perspectives

PROTOCOL TITLE: ATN 144 SMART

through collection of data from individual interviews. Foreseeable harms from participating in this study are not greater than those encountered in everyday life or during the performance of routine physical or psychological examinations or tests. In addition, in all 50 states and the District of Columbia, minors are explicitly permitted to consent for STI services without parental permission.

For children whose parents or legal guardians do not know about the children's HIV status and who if told would place the children at risk of harm, a waiver of parental permission for these children is requested. For children whose parents or legal guardians are aware of HIV status, but knowledge of participation in study would place the children at risk of harm, a waiver of parental permission for these children is requested. For children whose parents or legal guardians already know about the children's HIV status and who if told would not place the children at risk of harm, parental permission for these children will be obtained.

Procedures to Obtain/Waive Parental permission for YLH, age 15- 17.

The study team will put the following steps in place to ensure that parental permission for youth stakeholders, 15 – 17, is obtained or waived as set forth by the Institutional Review Board.

Screening procedures.

- The study screener will inform interested participants under the legal age (18) will need parental or legal guardian consent to be part of this study
- The study screener will inform prospective youths that although their parent's permission is usually required before children under the age of 18 may take part in the study, this permission will not be obtained for children who will be placed at risk of harm if their parents were told about their children's participation in this study.
- The screener will ask youth under 18 whether their parents or legal guardians know about their HIV status, and whether if told would will be placed at risk of harm.
- Youth who report that their parent is aware of their HIV status, they will be asked whether they will be placed at risk of harm if their parents were told about their participation in the study.
- Youth that indicate that they will *not* be at risk for harm, will be told that parental consent is required to participate in the study, and they must be able to comply with that requirement.
- Key study team members will review these youth's responses in the screener to ensure and document that only for children who indicated risk of harm was parental permission not obtained.

Consenting Procedures.

- The youth consent/assent form include a section to obtain parental consent for youth under 18 who will be not placed at risk of harm
- This section on the consent/assent form will inform youth under 18, who will not be placed at risk of harm that parental permission is required to take part

PROTOCOL TITLE: ATN 144 SMART

in the study and includes 2 questions to allow parental permission to be obtained.

The study team will ensure that youth whose parents or legal guardians already know about the children's HIV status and who if told would not place the children at risk of harm, parental permission for these children will be obtained.

The study team will review and document youth stakeholders' who whose parents or legal guardians do not know about the children's HIV status and who if told would place the children at risk of harm, a waiver of parental permission for these children is requested. For children whose parents or legal guardians are aware of HIV status, but knowledge of participation in study would place the children at risk of harm, a waiver of parental permission for these children is requested.

Additionally, the study team will ensure to review and document that study screener information and consent/assent forms are completed appropriately for all youth and document youth that indicate they would be at risk for harm. For every jurisdiction in which the study will be conducted and for which parental permission will not be obtained for one or more of the youth under the age of 18, waiving parental permission for these youth is not inconsistent with the state law in those jurisdictions in which the study will be conducted.

